## **Study Timeline**

The following chart lists the standard of care for treatment of patchy pediatric alopecia with ILTA. Each visit can be completed within + 7 days of the target date. Screening and baseline visits can be completed on the same day if appropriate.

	Screening	Baseline	5	Study Perio	d
Visit	V1	V2	V3	V4	V5
Week	-4-0	0	4	8	12
Estimated time requirement of visit	1 hour	1.5 hour	30 min	30 min	30 min
Informed Consent	X				
Inclusion/Exclusion Criteria	X	х			
Demographic Data	X				
Past medical and surgical history	X				
Alopecia Areata History	X				
Medications	X				
Allergies	X				
Vital signs (plus height and weight)	X	Х			
Full Skin Examination	X				
Limited Skin Examination		Х	X	X	X
Laboratory assessments	_				
Urine pregnancy test*	X	Х	X	X	Х
Intralesional triamcinolone acetonide		Х	X	X	Х
Photographs		X	X	X	Х
Adverse events		X	X	X	Х
Concomitant medications	_	х	X	X	Х
Efficacy Assessment	X	Х	X	X	Х
Pain Assessment		Х	X	X	Х
Quality of Life Assessments		Х	X	X	X
Patient Survey	· · · · · · · · · · · · · · · · · · ·	X	X	X	X

\*Required for all persons of childbearing potential at each visit.

## Data to be Collected

- Personal information (name, address, contact information, social security number)
- Medical records
- Personal medical history including medications and allergies
- Vital signs and physical exam findings
- Photographs
- Pregnancy laboratory test results if person of child-bearing potential
- Safety Data (Reported AEs)
- Efficacy Data (tPGA, pruritus score)
- Tolerability Data (Pain Score)
- Quality of life Data (DLQI, Patient survey)

## Data Analysis Plan

Statistical analyses will be completed under the supervision of a statistician. Statistical analysis will be done by statistical software (e.g. SPSS, SAS, R, Excel; etc.) AUROC will be calculated in order to assess for accuracy. The  $\chi^2$  test may be used for comparison of dichotomous variables, and the Mann-Whitney test may be used for non-normally distributed continuous variables. The cutoff value for significance was set at p = 0.05.

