## Objectives

- Primary Objectives
  - Validate patient tolerability of needle-free delivery of intralesional triamcinolone using patient-reported outcome measures.
- Secondary Objectives
  - Validate efficacy of needle-free delivery of intralesional triamcinolone for pediatric alopecia areata.
  - Assess the impact of needle-free delivery of intralesional triamcinolone on quality of life for pediatric alopecia areata.

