## **Number of Research Participants**

This is a proof-of-concept pilot study. Collins et al. stated that the boundary between mild and moderate pain is a numerical rating scale (NRS) score of 3 (Collins 1997). Previous use of needle-free delivery methods have demonstrated an NRS < 3 (Nantel-Batista 2017, Vadeboncoeur 2017). Based on previous studies and the pilot nature of this study, 15 subjects will be enrolled to determine whether mild or moderate pain would be anticipated in future large scale assessments.

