## **Study Design**

This is an interventional pilot study assessing the tolerability of needle-free delivery administration of ILTA with the Med-Jet as an alternative to conventional syringe and needle in patients with patchy pediatric alopecia areata. There will be a total of four (4) or five (5) visits necessary for study participation. We hypothesize that the Med-Jet will have acceptable pain tolerability, efficacy, safety, and a positive impact on patient quality of life.

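### The only method the analysis plan commits to, an AUROC, is undefined, and no stated analysis addresses whether pain lies below or above NRS 3

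*Combined protocol and SAP*

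**What the plan says.** The Data Analysis Plan of the combined protocol and SAP is a single paragraph. It commits to one method: "AUROC will be calculated in order to assess for accuracy". It then allows two more: the chi-square "test may be used for comparison of dichotomous variables", and "the Mann-Whitney test may be used for non-normally distributed continuous variables". It sets significance at 0.05. It names no endpoint, comparison groups, visit or summary measure, and it does not mention pain.

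The rest of the document sets a different task. The primary objective is "Validate patient tolerability of needle-free delivery of intralesional triamcinolone using patient-reported outcome measures". The Number of Research Participants section cites a source for the statement that "the boundary between mild and moderate pain is a numerical rating scale (NRS) score of 3", and gives the reason for the sample: "15 subjects will be enrolled to determine whether mild or moderate pain would be anticipated in future large scale assessments". The Study Design section adds "We hypothesize that the Med-Jet will have acceptable pain tolerability, efficacy, safety, and a positive impact on patient quality of life". The Data to be Collected list identifies the pain score as the tolerability data.

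The measurements are within child. Pain is rated on Wong-Baker FACES and on a 0-10 NRS before and after each procedure (Pain Score Assessment). One patch is treated (intervention text under Prior and Concomitant Medications and Therapies) and has a comparator patch in the same child (Clinical Assessments). A survey at each visit also covers perceived tolerability and fear (Patient Survey). There is no needle-and-syringe arm.

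**The concern.** An AUROC needs a score and a binary condition for that score to discriminate. The documents define neither, and no objective concerns accuracy. The two optional tests do not fill the gap. Mann-Whitney compares two independent samples, and the document describes one treated group. The chi-square is mentioned without a dichotomy or a reference proportion.

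At stake is the one result the pilot is meant to pass on, namely whether later studies should expect pain below or above NRS 3. If the plan is followed literally, nothing in it produces that result. If it is filled in afterwards, the visit (there are up to four with injections) and the side on which a score of exactly 3 falls can both be settled with the data in view. Either choice can change the answer.

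**Working it through.** **Inputs from the documents.** N = 15 and boundary 3 (Number of Research Participants); NRS 0-10, before and after (Pain Score Assessment); injections at up to four visits, weeks 0, 4, 8 and 12, omitted once regrowth is complete (Study Visits); an earlier needle-free mean of 2.1 (Drugs or Devices). **Assumptions**, because the documents give no values: SD 1.5, 2 or 2.5; within-child correlation 0.3 to 0.7.

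There is no figure of the plan's own to reproduce. The 15 is stated without SD, power or margin.

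1. **Would an improvised AUROC answer the question?** Take before against after scores, with AUROC = U/(n1 × n2). Let all 15 before scores be 0. If the after scores are 1, 2 and 3 (five children each, mean 2), every one of the 15 × 15 = 225 pairs is ordered, so AUROC = 225/225 = 1.00. If they are 5, 6 and 7 (mean 6), AUROC is again 1.00. The Mann-Whitney p-value is 5.6 × 10⁻⁷ both times. Neither statistic separates a mean of 2 from a mean of 6. An AUROC of FACES against dichotomised NRS would describe how well one scale tracks the other, not where pain lies relative to 3.

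2. **Precision of the estimate that would answer it.** Half-width = t(0.975, 14) × SD/√15 = 2.145 × SD/3.873:
   - SD 1.5: 0.83; interval around 2.1 is 1.27 to 2.93
   - SD 2: 1.11; 0.99 to 3.21
   - SD 2.5: 1.38; 0.72 to 3.48

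   An interval around 2.1 excludes 3 when the half-width is below 0.9, that is, when SD < 0.9 × 3.873/2.145 = 1.63. As a proportion, 12/15 = 80% has an exact (Clopper-Pearson) 95% interval of 51.9% to 95.7%.

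3. **Effect of the unstated cut.** With beta-binomial scores on 0-10, means 2.1 and 3 and SD 1.5 to 2.5, between 8.6% and 25.7% of children score exactly 3 (15 × 0.086 = 1.3 to 15 × 0.257 = 3.9 children). At mean 3 and SD 1.5, the share called mild is 39.0% if mild means below 3 and 64.7% if it means 3 or below. At mean 2.1 and SD 2 the shares are 65.0% and 77.7%.

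4. **Effect of the unnamed visit.** In simulations (40,000 runs per setting) with 15 children all injected at four visits and a true mean of exactly 3 each time, the 95% interval lies wholly below 3 in 3.1% to 4.6% of trials at one named visit, and in 8.3% to 15.2% at one or more of the four. Averaging each child's visits gives about 3% to 4%, so the inflation comes from choosing a visit, not from having several.

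5. **Paired contrasts (secondary).** With normal data, n = 15, a 0.8 SD shift and correlation 0.5, power is 53.4% for Mann-Whitney and 80.1% for signed-rank, and Mann-Whitney's type I error is 0.9%. At correlation 0 power is 52.7% and 51.5%. Ignoring positive correlation therefore errs conservatively. Patch regrowth is recorded in six ordered categories, so these figures are only indicative.

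**The case against.** The strongest reply is that this is a 15-child proof-of-concept pilot with no confirmatory claim. A statistician will supervise, and a descriptive NRS summary could be drawn from data already being collected. That stands as mitigation: no power calculation or larger sample is called for. But pilot status does not excuse leaving the main tolerability measure without a specified analysis, and supervision is not pre-specification.

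Four stronger readings are tempting, and the documents do not support them.

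- A reader might infer that the AUROC is impossible to compute. It is undefined: one could be built from before and after scores or from the two pain scales, but the plan chooses neither.
- A reader might infer that mild versus moderate pain is the whole primary objective. That question sits in the sample-size section. The objective itself is tolerability by patient-reported measures in the plural, and FACES and the survey belong to it. Making NRS at one visit primary is a choice, though one consistent with the sample-size section and the data list.
- A reader might infer that both optional tests are wrong in themselves. Chi-square has a one-sample form; as written it is too vague to apply.
- A reader might take 8% to 15% as the trial's error rate. It holds only under the conditions in the verdict.

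The sample-size section describes earlier scores as below 3, which hints at a cut. The average of 3 reported for one of the same trials under Drugs or Devices blurs that hint.

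**Conclusion.** The point holds in this form: the sole committed method is undefined and serves no stated objective, the optional tests are attached to nothing, and no stated analysis places pain relative to NRS 3. That conclusion rests on the text alone and needs no assumption.

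The sizes do rest on assumptions. The half-width of about 0.8 to 1.4 depends on an SD of 1.5 to 2.5; a mean of 2.1 would exclude 3 only if the SD were below about 1.6. The cut figures depend on the beta-binomial shape. The visit figures (3% to 5% against 8% to 15%) apply only if the visit is chosen after the data are seen, all 15 children are injected at all four visits, and the true mean is exactly 3. The paired-test issue is secondary and does not threaten a false positive when scores are positively correlated. The paragraph should be replaced before any outcome data are examined.

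**What to change.** Replace the analysis paragraph:

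1. Delete the AUROC sentence.
2. Before data are seen, name post-procedure NRS at one injection visit as the primary tolerability measure. Report its mean with a 95% confidence interval set against 3, and the proportion below a stated cut with an exact 95% interval, saying on which side a score of exactly 3 falls. Present this as estimation.
3. Report FACES, the patient survey and NRS at the other injection visits descriptively as support, using only visits at which an injection was given.
4. State the precision of 15 children as worked out above, with the SD marked as an assumption.
5. For within-child contrasts, use Wilcoxon signed-rank or exact McNemar in place of Mann-Whitney or chi-square.
6. As a side point, reconcile the two descriptions of earlier pain scores (Number of Research Participants; Drugs or Devices).

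The cost is wording only: no new data, visits or participants.

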## • Study Visits

There will be four (4) or five (5) visits necessary for study participation:

- If all inclusion criteria are met and no exclusion criteria are met on the same day and the patient and their guardian wish to start the study, the baseline visit and screening visit can be completed on the same day. This will decrease the number of visits from 5 to 4. o
- If the patient has complete hair growth prior to the end of the study, they will complete all remaining visits, but they will not receive injections.
- Visit 1 Screening (within 5 weeks prior to baseline visit or same day, estimated time 1 hour if baseline activities are not performed):
  - We will obtain informed consent, review inclusion/exclusion criteria, obtain medical history (medical conditions, surgeries, alopecia areata history, medications, allergies, social history, and relevant family history), obtain vitals, perform a complete skin exam, efficacy assessments, patientreported pain assessments, and quality of life assessments. A urine pregnancy test will be performed for persons of childbearing potential.
- Visit 2 Baseline (Week 0, estimated time 1.5 hours if not performed the same day as screening):
  - This will be the in-office intervention visit to be scheduled within 4-6 weeks of screening visit. We will review inclusion/exclusion criteria, obtain concomitant medications, adverse events (AE), obtain vitals, perform limited skin examination with efficacy assessment, photograph of target lesions, perform intervention injections per protocol, collect patientreported pain assessments and quality of life assessments. A urine pregnancy test will be performed for persons of childbearing potential.
- Visits 3-5 Follow up study period (Week 4, 8, and 12, estimated time 30 minutes each):
  - A limited skin exam, photographs, review of AEs and concomitant medications, efficacy assessments, QoL assessments and pain assessments will be performed. ILTA will be administered at each visit unless complete regrowth has occurred. A urine pregnancy test will be performed for persons of childbearing potential.

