#### **Clinical Assessments**

- Physician Efficacy Assessments
  - Severity of Alopecia Tool (SALT) Score The SALT score is a visual tool to help assess percentage of hair loss on the scalp. The scalp is divided into four sections top, back, right side, and left side. Each section contributes to a total of 100% (i.e. top = 40%, back = 24%, sides = 18% each). Raters assess total percentage of hair loss in the section and then multiple is by the respective multiplier which is based on that sections total percentage of the scalp 40%, 24%, or 18%. Only terminal hairs are considered hair growth in this tool. (Olsen et al. 2004) Figure 1 illustrates the visual aid and allows for intuitive use. This is a static tool and only quantifies the hair loss at one point in time.
  - Alopecia Areata Investigator Global Assessment (AA-IGA) The AA-IGA categorizes the scalp hair loss into 5 categories based on the SALT score. The five categories are: 1 = None, 2 = Limited, 3 = Moderate, 4 = Severe, and 5 = Very Severe. The corresponding SALT scores for each category are: 1 = 0%, 2 = 1-20%, 3 = 21-49%, 4 = 50-94%, and 5 = > 95%. This is a static tool and only quantifies the hair loss at one point in time (Olsen 2004).
  - "Rule of Thumb" Assessment and Regrowth Categorization A patient's thumbprint projection is approximately 1% of the scalp surface area (King 2019). When selecting the alopecic patch for treatment and its comparator, thumb projections will be used to quantify the percentage of total scalp hair loss contributed by each these patches at baseline. At each subsequent visit, the thumbprint projection from baseline will be used to determine percent of regrowth since baseline. Based on regrowth, the patient will be categorized into one of 6 categories: A0-5. Where A0 = no change or further loss, A1 = 1-24% regrowth, A2 = 25-49% regrowth, A3 = 50-74% regrowth, A4 = 75-99% regrowth, and A5 = 100% regrowth.
- Patient-Reported Efficacy Assessments
  - Patient-Reported Hair Loss Whole Scalp This assessment will apply to the subject's whole scalp surface area. This question will be asked at every visit. And it will include 5 numerical categories: 0 = No missing hair (0% of my scalp is missing hair; I have a full head of hair); 1 = limited area (1% to 20% of my scalp is missing hair); 2 = moderate area (21% to 49% of my scalp is missing hair); 3 = large area (50% to 94% of my scalp is missing hair); and 4 = Nearly all or all (95% to 100% of my scalp is missing hair).

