## Pain Score Assessment

 Subjects will rate their pain using the Wong-baker FACES scale (Garra 2010) and a numerical rating scale (NRS) before and after the procedure. The NRS score ranges from 0-10 where 0 is no pain and 10 is the worst pain imaginable (Williamson 2005).

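### The only comparison tests named, chi-square and Mann-Whitney, are for independent groups, but this is a single group of 15 children whose contrasts lie within the child

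*Combined protocol and SAP*

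**What the plan says.** The Data Analysis Plan is one short paragraph. It names AUROC, a chi-square test for dichotomous variables, and states that "the Mann-Whitney test may be used for non-normally distributed continuous variables", with a significance cutoff of 0.05. It ties no test to an endpoint, contrast or visit, and it mentions no confidence interval.

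The rest of the protocol describes the data to be analysed:

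- **One group.** Under Study Design: "This is an interventional pilot study assessing the tolerability of needle-free delivery administration of ILTA". There is no parallel arm. Under Number of Research Participants: "15 subjects will be enrolled to determine whether mild or moderate pain would be anticipated in future large scale assessments".
- **Primary question.** The same section takes as its reference that "the boundary between mild and moderate pain is a numerical rating scale (NRS) score of 3".
- **Two patches in one child.** The Intervention text has one patch per child treated. Under Clinical Assessments: "When selecting the alopecic patch for treatment and its comparator, thumb projections will be used".
- **Pain twice per procedure.** Under Pain Score Assessment, children rate pain "before and after the procedure".
- **Repeated visits.** Study Visits and the Study Timeline schedule injections at week 0 and again at weeks 4, 8 and 12, so up to four sessions per child.

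The only visible between-child split is age 6-11 against 12-17. Those bands use different quality-of-life instruments, and no comparison between them is described.

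**The concern.** Mann-Whitney and the chi-square comparison of proportions both assume that the two sets of values come from different, unrelated subjects. Here both sets come from the same 15 children. Applied to pairs, the tests ignore the correlation that the within-child design exists to exploit, and with so few children that loss of power could hide a real difference between treated and comparator patches. If rows from several visits were stacked, each child would be counted several times. For the primary question of whether pain lies below or above NRS 3, neither test applies even at a single visit.

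**Working it through.** **The plan's own figure.** The sample size of 15 rests on "Based on previous studies and the pilot nature of this study". No SD, power, target difference or dropout is given, so there is nothing to reproduce.

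**Inputs.** From the protocol: n = 15 children, up to 4 sessions, cutoff 0.05 (two-sided assumed). The documents give no correlations or variance shares; all those below are assumptions, shown as ranges. The simulations use normal data.

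**1. Pairs at one visit, continuous outcome.** With within-child correlation ρ, the difference in means has variance 2σ²(1−ρ)/n. An unpaired test assumes 2σ²/n. The ratio of true to assumed variance is 1−ρ, that is 0.7, 0.5 and 0.3 at ρ = 0.3, 0.5 and 0.7, so the unpaired test rejects too rarely. Simulation confirms this:

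| ρ | Mann-Whitney type I error | Mann-Whitney power, 0.7 SD shift | Signed-rank power, 0.7 SD shift |
|---|---|---|---|
| 0.3 | about 2% | about 40% | 55% |
| 0.5 | about 1% | about 40% | 69% |
| 0.7 | about 0.1% | about 40% | 88% |

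The signed-rank test holds its type I error at 4% to 5% throughout.

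**2. Pairs at one visit, dichotomous outcome.** With 15 pairs and a 40% rate on both sides, uncorrected chi-square rejects 2.7%, 2.0% and 0.9% of the time at latent correlations 0.3, 0.5 and 0.7. This is again conservative. Exact McNemar is also conservative (1.2%, 0.9%, 0.4%) and gains no power: with rates of 75% and 30% and latent correlation 0.5, it has 66% against 74% for chi-square.

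**3. Visits pooled as independent rows (not stated in the plan).** The direction now depends on the contrast.

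- *Pain against NRS 3, 15 × 4 = 60 ratings.* The design effect is 1 + 3 × ICC = 1.9, 2.5 and 3.1 at ICC 0.3, 0.5 and 0.7, so 60 ratings carry the information of 60/1.9 ≈ 32, 60/2.5 = 24 and 60/3.1 ≈ 19. A one-sample t-test on the pooled rows has type I error of 15%, 22% and 28%.
- *Pain before against after, 60 v 60.* With a shared child effect and independent residuals, Mann-Whitney rejects 2.3%, 1.0% and 0.1% at child shares of 0.3, 0.5 and 0.7. This is conservative.
- *Treated against comparator patch, k visits.* Write the variance shares as child, patch within child, and residual. The ratio of true to assumed variance of the difference in means is k × patch share + residual share; above 1 the test is liberal, below 1 conservative. With k = 4:
  - shares 0.5/0/0.5 give a ratio of 0 + 0.5 = 0.5 and 1% false positives;
  - shares 0.5/0.2/0.3 give 0.8 + 0.3 = 1.1 and 7%;
  - shares 0.1/0.6/0.3 give 2.4 + 0.3 = 2.7 and 24%.

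  With only the three follow-up visits (k = 3, 45 v 45):
  - shares 0.6/0.1/0.3 give 0.3 + 0.3 = 0.6 and 1.9%;
  - shares 0.3/0.4/0.3 give 1.2 + 0.3 = 1.5 and about 12%;
  - shares 0.2/0.6/0.2 give 1.8 + 0.2 = 2.0 and about 17%.

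**The case against.** Each test only *may* be used, neither is assigned to an endpoint, and a statistician supervises. So this is under-specification rather than a stated intention to run Mann-Whitney on pairs. It is also a 15-child proof-of-concept pilot with no confirmatory decision tied to the 0.05 cutoff, and at one visit with positive correlation the named tests err only on the conservative side.

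Much of this stands, and it limits what can be claimed. A reader might infer more than the documents support:

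- *That every comparison is paired or repeated.* The primary pain question is one-sample; repetition enters only if several visits are used.
- *That p-values and intervals will be wrong in both directions.* The plan assigns no test to a contrast and plans no interval. The inflated error rates all require visits to be pooled as independent rows, which the plan does not say it will do.
- *That pooling always inflates false positives.* It does not for pain before against after, and for the patch contrast the sign depends on undocumented variance shares.
- *That McNemar would recover power.* At 15 pairs it does not; the reason to use it is validity for paired data.

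The permissive wording still does not cure the gap. No valid alternative is named anywhere, and supervision is not a pre-specified method. Pilot status does not make an independent-groups test suitable for pairs when the plan itself sets a significance cutoff.

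**Conclusion.** The point holds in this form: the plan names only independent-group comparison tests, and neither fits any contrast that the design describes. The firm consequence is at a single visit. Mann-Whitney on the 15 pairs would run at about 2% to 0.1% instead of 5%, with about 40% power for a 0.7 SD shift where the signed-rank test has 55% to 88%, over assumed correlations of 0.3 to 0.7. The conditional consequence, if visits were pooled as independent rows, is an error of either sign: about 1% to 24% false positives for the patch contrast over the assumed variance shares, and 15% to 28% for pain against NRS 3 at ICC 0.3 to 0.7. The exact sizes rest on normal data and on correlations that the documents do not give. The mismatch between tests and design does not. It should be corrected before any analysis.

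**What to change.** Replace the test sentence in the Data Analysis Plan so that it:

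- gives, for the primary pain question, a one-sample estimate with a 95% interval set against NRS 3, at a named visit;
- analyses paired ordinal or continuous outcomes by the Wilcoxon signed-rank test on each child's difference, with a Hodges-Lehmann 95% interval;
- analyses paired dichotomies by exact McNemar;
- uses, where several visits enter, one summary per child or a mixed model with a random child effect, and otherwise names the visit analysed;
- states that N is the number of children, not of sessions or patches.

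The Intervention text says that a single patch is treated, but its procedure paragraph speaks of injecting patches in the plural. These statements must be reconciled, because the treated-against-comparator contrast depends on them.

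The cost of the analysis change is plan wording only: no extra children, visits or data.

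### One p = 0.05 cutoff covers eight secondary measures at three follow-up visits, with no lead measure, lead visit or descriptive-only status, so the false-positive risk is inflated by an undetermined amount

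*Combined protocol and SAP*

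**What the plan says.** The Data Analysis Plan is one short paragraph. Its only error-rate statement is "The cutoff value for significance was set at p = 0.05". It offers the chi-square test for dichotomous variables, says that "the Mann-Whitney test may be used for non-normally distributed continuous variables", and mentions an AUROC. None of these is tied to a measure, a comparison or a visit. It does not give the sidedness of the tests, any hierarchy or adjustment, or a statement that secondary results are descriptive.

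The Objectives section has two secondary objectives: "Validate efficacy of needle-free delivery of intralesional triamcinolone for pediatric alopecia areata" and "Assess the impact of needle-free delivery of intralesional triamcinolone on quality of life for pediatric alopecia areata". Neither picks a measure or a time point.

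The measures available to serve them are:

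- **Physician-rated efficacy** (Clinical Assessments): SALT; AA-IGA, where "The AA-IGA categorizes the scalp hair loss into 5 categories based on the SALT score"; and the Rule of Thumb regrowth category, where "Based on regrowth, the patient will be categorized into one of 6 categories: A0-5".
- **Patient-reported efficacy** (Clinical Assessments): whole-scalp hair loss, whole-scalp regrowth, and regrowth of the selected patches.
- **Quality of life** (Quality of Life Assessment): the children's index at ages 6-11 and the T-QoL at ages 12-17.

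The Study Timeline has these assessments at all three follow-up visits (Weeks 4, 8 and 12). Number of Research Participants sets 15 subjects, calls the study a proof-of-concept pilot, and justifies the number on pain alone.

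**The concern.** The plan leaves open which secondary result, at which visit, will answer the efficacy objective. If the choice is made after the data are seen, a single p-value below 0.05 among many can be presented as meeting an objective that is worded as validation. Data to be Collected widens the choice: it lists a tPGA and a pruritus score as the efficacy data, and neither appears in Clinical Assessments.

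A second problem adds to the first. SALT, AA-IGA and the two patient-reported whole-scalp ratings have no untreated comparator. Background estimates that 80% of limited, patchy cases recover spontaneously, without saying over what period. A before-after test on a whole-scalp rating could therefore be significant with no treatment effect, and no multiplicity adjustment would correct that.

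At stake is how far a later trial could rely on an efficacy statement from this pilot.

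**Working it through.** **Nothing to reproduce.** The 0.05 cutoff stands alone. The plan states no number of tests, familywise error rate or power.

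**Inputs from the documents.** Alpha is 0.05 (Data Analysis Plan). There are 6 efficacy ratings and 2 quality-of-life indices, so 8 measures (Clinical Assessments; Quality of Life Assessment), at 3 follow-up visits (Study Timeline). The most measure-by-visit tests is 8 × 3 = 24. The patient survey, which Data to be Collected places under quality of life, is not counted.

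**Assumptions not in the documents.** Tests are two-sided, so 0.025 lies in the favourable direction. Each test holds its nominal level. All the tests counted are run. Correlations are as stated below.

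**Step 1: independent tests.** P(at least one significant) = 1 − 0.95^m. P(at least one significant and favourable) = 1 − 0.975^m.

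| Tests m | Any result | Favourable result |
|---|---|---|
| 1 | 5.0% | 2.5% |
| 8 (one visit) | 33.7% | 18.3% |
| 14 | 51.2% | 29.8% |
| 24 (three visits) | 70.8% | 45.5% |

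Under independence it takes 14 tests before any significant result becomes more likely than not. A favourable one stays below 50% even at 24.

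**Step 2: correlated tests.** AA-IGA is computed from SALT, and the same children are rated repeatedly, so independence is only a ceiling. For 24 normal test statistics, 200,000 draws were simulated with a common correlation between measures and a common correlation between visits. The correlation between different measures at different visits is the product of the two. The threshold was 1.96.

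| Between measures / between visits | Any result | Favourable result |
|---|---|---|
| 0.5 / 0.5 | 52.8% | 27.5% |
| 0.7 / 0.7 | 37.0% | 18.6% |
| 0.9 / 0.9 | 18.8% | 9.3% |

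Each child completes only one quality-of-life index. Treating the two indices as independent of each other and of the efficacy block gives 30.5% to 58.0% for any result and 16.0% to 32.4% for a favourable one, over correlations of 0.9 to 0.5.

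**Step 3: the named test on paired data.** Treated and comparator patches lie in the same child. A Mann-Whitney test that ignores the pairing, on 15 pairs, rejects under the null 4.6% of the time at within-pair correlation 0, 1.0% at 0.5 and 0.2% at 0.7. If all 24 tests were independent and behaved this way, the chance of any significant result would be 1 − 0.99^24 = 21% at correlation 0.5 and 1 − 0.998^24 = 5% at 0.7. Steps 1 and 2 therefore apply to tests that hold their 5% level, as suitable paired tests would.

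**Step 4: under the fix.** With one lead measure at one visit, a test of it would carry 5% two-sided, or 2.5% favourable. The 95% interval for a mean within-child difference with all 15 children has half-width t(0.975, 14)/√15 = 0.55 standard deviations of the differences.

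**The case against.** The strongest reply is that the 24 tests are not in the plan. The Data Analysis Plan lists no comparisons and says only that certain tests may be used. Collecting data at three visits does not commit anyone to testing at each. This stands: 24 is a ceiling, not a planned number.

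A reader might go further and infer that a chance validation of efficacy or quality of life is likely. The documents do not support that, for three reasons. No section says that one significant result out of many meets the objective. A chance validation would have to be favourable, and that probability is below 50% even for 24 independent tests. And validation is the wording for efficacy only; for quality of life the objective is to assess impact.

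It can also be said that Mann-Whitney on paired data is conservative, so literal use of the named test would shrink or even remove the inflation (step 3). That is true, but it is a separate mismatch between test and design. It would cost power, and it is no safeguard if a suitable paired test is used instead.

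Finally, strict familywise control of secondary measures is not normally expected of a 15-child pilot whose primary objective is tolerability. This also stands, and none is asked for here. Pilot status would settle the matter if the plan called its secondary results exploratory, but it does not, and it keeps both a significance cutoff and a validation objective.

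**Conclusion.** The concern holds in a limited form. The plan names no lead secondary measure, no lead visit and no descriptive-only status. For tests that hold their 5% level, the chance of at least one false-positive secondary result therefore exceeds the nominal level by an amount that cannot be worked out from the plan.

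The ceiling is 71% for any significant result and 46% for a favourable one, if all 24 tests are run and independent. With assumed correlations of 0.5 to 0.9 the figures are about 53% down to 19%, and 28% down to 9%. These rest on two-sided testing and on assumed correlations. They describe the room for a chance finding, not a prediction that one will be claimed. The missing comparator for whole-scalp ratings is an additional weakness that these figures do not include.

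**What to change.** In the Data Analysis Plan, name one lead efficacy estimate: the Week 12 within-child difference in regrowth, treated minus comparator patch, analysed as paired data with a 95% interval. State that all other efficacy and quality-of-life measures and visits will be reported as estimates with 95% intervals and no significance wording. In the Objectives section, change *Validate* to *Estimate* in the secondary efficacy objective.

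The data for the lead estimate are already due to be collected: under Intervention only one patch is treated, and Clinical Assessments quantifies that patch and its comparator. Two limits should be acknowledged. The protocol does not say how the patch to be treated is chosen, so the difference accounts for spontaneous regrowth only as far as the two patches are comparable. And the procedure text under Intervention speaks of injecting patches in the plural, which must be reconciled with the one-patch statement.

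The cost is wording only, with no added visits, children or assessments. What is given up is any claim of significance on the other measures.
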